6.2.2.2.1 Analysis Methods

The hypothesis will be tested at the 2.5% significance level.

[REDACTED]

The null hypothesis will be rejected if the upper limit of the 1-sided, 97.5% CI for the HR of Post-Implant to Pre-Implant is less than 1.

6.2.2.3 Individual Components of the Primary Endpoint

6.2.2.3.1 HFH at 12 months Post-Implantation

[REDACTED]

6.2.2.3.2 HFH Equivalents at 12 months Post-Implantation

[REDACTED]

6.2.2.3.3 All-Cause Mortality at 12 months Post-Implantation

[REDACTED]

[figure not shown]
6.2.2.4 Secondary Safety Endpoint: Freedom from DSRCs over 12 Months Post-Implantation

[REDACTED]

6.3 Justification of Clinical Trial Design

The Randomized Arm will evaluate the effectiveness of HF management using the CardioMEMS™ HF System by comparing outcomes against HF management on the basis of standard of care alone. The Randomized Arm is a prospective, randomized, controlled, single-blind investigation, providing the highest level of evidence (26, 27) to expand the indication for the CardioMEMS™ HF system to patients with elevated NT-proBNP (or BNP) or NYHA Class II or Class IV.

[REDACTED]

The Single Arm is a prospective, multi-center, clinical trial of the CardioMEMS™ HF System in NYHA Class III HF patients with either elevated NT-proBNP (or BNP) levels and/or a prior HFH. It will be used to demonstrate equivalence of clinical outcomes between NYHA Class III subjects with an elevated NT-proBNP (or BNP) only and those with a prior HFH only. Results of this clinical trial will be used to support an expanded indication to subjects with elevated NT-proBNP (or BNP) for NYHA Class III patients.

The primary effectiveness endpoint of both the Randomized Arm and Single Arm, the composite of HF events and mortality, is a clinically relevant endpoint for HF patients, and has been used in previous IDE trials (6, 8) and was recommended for use in future clinical trials by consensus among HF experts (28).

[figure not shown]
The secondary effectiveness endpoints of the Randomized Arm (not including the individual components of the primary endpoint) were selected for the following reasons:

- Change in EQ5D-5L – Use of EQ5D in cardiovascular studies has increased in recent years and published studies provide evidence of its validity and reliability (29). The EQ5D-5L was shown to have better measurement properties than the original EQ5D (30).
- Change in KCCQ-12 – This instrument has been shown to be a valid, reliable, responsive, and prognostically important measure of health status for HF patients (31).
- Improvement in 6MHW test – In congestive HF patients, the 6MHW test provides an objective assessment of exercise capacity that supplements clinical information obtained from medical history and physical examination (32).

The secondary endpoint of the Single Arm (not including the individual components of the primary endpoint), the comparison of HFH in the 12 months prior compared to the 12 months post-implantation, was selected as it provides an objective measure of whether individual hospitalizations have decreased compared to pre-implantation and has been used in prior retrospective analyses in similar patient populations (12).

The secondary safety endpoint for both the Randomized Arm and Single Arm were selected as it has been used in previous IDE and post-approval trials for implantable hemodynamic monitoring devices, including the CardioMEMS™ HF System.

6.4 Multiplicity

6.5 Overall Sample Size

The overall sample size required for evaluation of the Randomized Arm and Single Arm primary endpoints is approximately 3600 (1000 (successfully implanted and randomized) for the Randomized Arm and 2600 (successfully implanted) for the Single Arm). [REDACTED]

6.6 Statistical Criteria for Termination

There are no statistical criteria for termination of this trial.

6.7 Deviations from Statistical Plan

If any deviations from the original statistical plan occur, such deviations will be documented in the clinical trial report or statistical report containing the analysis results.

7 Risks and Benefits

The risks associated with the CardioMEMS™ HF System can be found in the CardioMEMS™ System User Manual. The trial does not require any additional procedures or assessments over the standard of care being used in the currently indicated population. Although this trial will evaluate the CardioMEMS™ HF System in a patient population that is different than the currently indicated population, there are no anticipated additional risks introduced to trial subjects.

7.1 Risks Associated with the Device under Investigation

The following list of anticipated AEs is outlined in the CardioMEMS™ IFU from past clinical experience. In addition, the list includes the most common events observed and/or documented in the literature associated with HF and CardioMEMS™ HF System implant and exposure.

7.1.1 Anticipated AEs

Events associated with the CardioMEMS™ PA Sensor or the implant procedure (in conjunction with RHC) or post-implantation complications are considered anticipated and include the following:

- Infection
 - Upper respiratory infection
 - Bronchitis
 - Pneumonia
 - Acute Bronchitis
 - Groin abscess
 - Methicillin-resistant staphylococcal aureus infection
 - Pulmonary Infiltration
 - Sepsis
- Arrhythmias
 - Ventricular tachycardia
 - Atrial fibrillation
 - Ventricular arrhythmia
 - Ventricular fibrillation
 - Atrial fibrillation with rapid ventricular response
 - Atrial flutter
 - Cardiac dysrhythmias
 - Tachycardia
 - Wide complex tachycardia

- Bleeding
 - Epistaxis
 - Hemoptysis
 - GI bleed
 - Bleeding
 - Blood in stool
 - Catheter site bleeding
 - Catheter site ecchymosis
 - Hematuria
 - Nose bleeds
- Hematoma
 - Hematoma
 - Catheter site hematoma
 - Vessel puncture site hematoma
- Thrombus
 - Arterial thrombosis (limbs)
 - Blood clot
- Myocardial infarction
- Transient ischemic attack
- Stroke
- Death
- Sensor embolization
- Pulmonary artery perforation

Refer to the CardioMEMS™ PA Sensor and Delivery Catheter, Model CM2000 User Manual for more information. If there are any questions regarding whether an event meets the associated definition (see Appendix C), the in-house Sponsor contact should be consulted.

7.1.2 Anticipated ADEs/SADEs

The following is a list of possible anticipated ADEs/SADEs:

- Hemoptysis
- Sensor not deploying
- Transient ischemic attack
- Atypical chest pain
- Sepsis leading to death
- Atrial arrhythmia leading to death
- Arterial embolism (upper extremity)
- PA (in-situ) thrombus
- Catheter site bleeding
- Catheter site ecchymosis
- Catheter site hematoma
- Vessel puncture site pain
- Cardiac monitoring abnormal
- Heart rate irregular
- Serum creatinine increased
- Dyspnea
- Congestive HF
- Ventricular tachycardia
- Dizziness
- Vessel perforation
- Sensor failure/malfunction
- Sensor migration

- System not transmitting

7.1.3 Non-AE Device Issue

To adequately capture non-AE device issues, any device issues that fall outside of the AE definition (see Appendix C), a separate form will be used to capture such instances when the device fails to perform or does not function properly without an associated an adverse clinical outcome.

7.2 Risk Control Measures

Every possible effort will be taken to minimize the risks, including:

- Careful selection of experienced Investigators for the clinical trial
- Early (within 60 days of the first enrollment) and adequate monitoring for each clinical trial site per the trial monitoring plan
- Conducting the clinical trial in accordance with the CIP, all applicable laws and regulations and any conditions of approval imposed by the appropriate IRB/EC or applicable regulatory authorities where the clinical trial is performed
- Preparation of the CardioMEMS™ PA Sensor and performance of the implantation procedure in accordance with the IFUs
- Training of Investigators both on the CIP and the CardioMEMS™ PA Sensor implantation procedure
- Securing compliance of non-compliant sites (see section 11.3)
- Assessment of continuing safety of subjects in the clinical trial by a DSMB

7.3 Possible interactions with concomitant treatments

The CardioMEMS™ PA Sensor is implanted in the PA via entry through the right side of the heart. If other device right heart leads are previously implanted, it is possible to cause dislodgement. Care should be taken to perform the implant procedure under fluoroscopy.

7.4 Anticipated Benefits

The benefit of hemodynamic-guided HF management in this population is unknown and information will be learned from this trial. Subjects with NYHA Class III HF and a prior HFH studied in the Treatment Group of the CHAMPION™ trial experienced a reduction in HF admissions. However, there is no guarantee that a similar benefit will occur in this slightly different population of NYHA Class II, III, or IV HF patients with a prior HFH and/or elevated NT-proBNP (or BNP). The information gathered will provide additional evidence regarding hemodynamic-guided HF management in at-risk NYHA Class II, III, or IV HF patients.

7.5 Risk-to-Benefit Rationale

Congestive HF is a progressive disease and HF patients are generally symptomatic. Symptoms of dyspnea and fatigue increase with elevations of pressures within the heart and lungs, leading to instances of acute HF decompensation. The CardioMEMS™ HF System enables clinicians to medically manage HF patients by adjusting treatments to keep PA pressures within target ranges to prevent or reduce instances of acute HF decompensation. In doing so, the CHAMPION™ trial demonstrated a reduction in rates of HF decompensation resulting in an HFH in NYHA Class III patients who had a HFH within the prior 12 months. Treating with the knowledge of PA pressures may extend benefit to this at-risk population of HF patients with the goal of reducing decompensation events that result in HFHs or emergency department/hospital outpatient visits requiring intravenous diuretic therapy. The trial is designed to demonstrate this benefit to an expanded patient population.

7.6 History of Device Modifications or Recall

There have been no modifications or recall in relation to safety and clinical performance of the CardioMEMS™ HF System under investigation.

8 Requirements for Investigator Records and Reports

8.1 Deviations from CIP

A deviation is defined as an instance of failure to follow, intentionally or unintentionally, the requirements of the CIP. The Investigator should make every effort not to deviate from the CIP, and all deviations must be reported.

If a subject is successfully implanted and/or randomized, but later found to not meet all inclusion/exclusion criteria, the subject will remain enrolled and a protocol deviation must be submitted.

Additionally, in the event that the IFU is not followed and an alternative implantation approach is pursued, the alternative implantation approach and associated justification must be reported as a protocol deviation. The Sponsor will review and track deviation frequency and trends. All effort should be made to avoid deviations, and repeat offense will result in Sponsor intervention (see section 11.3). Deviations are expected to be infrequent.

In some cases, failure to comply with the CIP may be considered failure to protect the rights, safety and well-being of subjects; such non-compliance exposes subjects to unreasonable risks. Examples include failure to comply with prescribed clinical trial procedures with respect to: obtaining ICF properly, performing assessments within the applicable time period, following the CardioMEMS™ PA Sensor implantation procedure, following treatment guidelines (without documentation of the reason), following subject contact procedures (for the Randomized Arm), adhering to the inclusion/exclusion criteria, and reporting device-related AEs. Investigators should seek to minimize such risks by adhering to the CIP.

The PI must maintain accurate, complete, and current records, including documents showing the date of and reason for each deviation from the CIP. Relevant information for each deviation will be documented as soon as possible on the applicable CRF, and submitted by the site to the Sponsor.

The PI is required to adhere to local regulatory requirements for reporting deviations to IRB/EC.

An Investigator shall notify the Sponsor and the reviewing IRB/EC of any deviation from the investigational plan to protect the life or physical well-being of a subject in an emergency. Such notice shall be given as soon as possible, but no later than five working days after the emergency occurred. Except in such an emergency, prior approval by the Sponsor is required for changes in or deviations from the CIP, and if these changes or deviations may affect the scientific soundness of the CIP or the rights, safety, or welfare of human subjects, FDA and IRB/EC is also required.

8.2 Safety Reporting

Safety surveillance and the safety reporting by the Investigator starts as soon as the subject is enrolled (all entry criteria are met, informed consent is provided, and implantation of the CardioMEMS™ PA Sensor is attempted) in either the Randomized Arm or the Single Arm.

Safety surveillance and safety reporting will continue until the last investigational visit has been performed, the subject is deceased, the subject's participation in the clinical trial is concluded by the Investigator, or the subject withdraws from the clinical trial.

All reportable (per section 8.2.1) AE data including deaths will be collected throughout the clinical trial and will be reported to the Sponsor on the applicable CRFs.

Reportable AEs will be monitored until they are adequately resolved or the subject has ended his/her participation in the trial, whichever comes first. The status of the subject's condition will be documented at each visit.

See *Appendix C* for event definitions regarding safety reporting.

SAE Reporting

The investigator should report all SAEs to the Sponsor as soon as possible but no later than outlined below.

Clinical Site	Reporting timelines
All Sites	SAEs must be reported to the Sponsor no later than 3 calendar days from the day the site personnel became aware of the event or as per the investigative site's local requirements, if the requirement is more stringent than those outlined.

The date the site staff became aware the event met the criteria of an SAE must be recorded in the source document. The Investigator will further report the SAE to the local IRB/EC according to the institution's IRB/EC reporting requirements.

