3.1.2 Device Description and Intended Purpose

The CardioMEMS™ HF System is currently indicated for wirelessly measuring PA pressure and heart rate to guide HF management in NYHA Class III HF patients who have been hospitalized for HF in the previous year. The resultant hemodynamic data are used by clinicians for HF management with the goal of reducing HFHs. The CardioMEMS™ HF System received FDA approval for that indication on May 28, 2014. The GUIDE-HF trial will evaluate the use of the CardioMEMS™ HF System for wirelessly measuring PA pressure to guide HF management in NYHA Class II, III, or IV HF patients who have been hospitalized for HF or who have elevated NT-proBNP (or BNP).

The CardioMEMS™ HF System provides PA hemodynamic data to monitor and manage HF patients. The CardioMEMS™ HF System measures PA pressure which clinicians use to initiate or modify HF treatment.

The CardioMEMS™ HF System includes the following components:

- CardioMEMS™ PA Sensor and Delivery Catheter
- CardioMEMS™ Hospital Electronic Unit
- CardioMEMS™ Patient Electronic Unit
- Merlin.net™ (patient database website)

The implantable CardioMEMS™ PA Sensor measures PA pressure using Micro-ElectroMechanical System (MEMS) technology, which enables powering of the implanted sensor via external interrogation thus removing the need for batteries or leads. It is fabricated using silicon wafers and measures 15 mm in length, 3.4 mm in width and 2 mm in thickness.

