4.1.2 GUIDE-HF Randomized Arm

The GUIDE-HF Randomized Arm is a prospective, multi-center, randomized, controlled, single-blind clinical trial of the CardioMEMS™ HF System in NYHA Class II, III, or IV HF patients with either elevated NT-proBNP (or BNP) and/or a prior HFH. The trial will be conducted in 140 sites across North America. After screening procedures and signing the Informed Consent Form, subjects will complete baseline assessments. Within 60 days of consent, subjects will receive a CardioMEMS™ HF System and, within 24 hours of implantation, be randomized in a 1:1 ratio into one of two groups:

- **Treatment Group:** Management of subjects based on PA pressure information derived from the CardioMEMS™ HF System
- **Control Group:** Management of subjects per standard of care (signs, symptoms, weight etc.) without knowledge of PA pressure information derived from the CardioMEMS™ HF System

Subjects will be considered enrolled in the Randomized Arm once all entry criteria are met, informed consent is provided, and implantation of the CardioMEMS™ PA Sensor is attempted. Safety information and adverse events (AEs) will be reported (per section 8.2) for all enrolled subjects. However, subjects will only contribute towards the sample size and primary, secondary effectiveness, and descriptive endpoint analyses following successful implantation and randomization.

No subject in the trial, regardless of treatment group, will have direct access to their uploaded PA pressure information. Investigators and clinical trial personnel will not have access to uploaded pressure information for subjects in the Control Group. Efforts will be made to ensure that subjects in the Treatment and Control Groups of the Randomized Arm will have communications with the sites at a similar frequency, using only a pre-specified telephone script. Both Treatment and Control Group subjects will be contacted at least once every two weeks for the first three months post-implantation, and at least monthly from three months until the 12 month follow-up visit.

[REDACTED]

The GUIDE-HF Randomized Arm will include approximately 1000 subjects (following successful implantation and randomization, 500 per group) at approximately 140 sites. Each subject will be followed for 12 months, with follow-up visits at 6 and 12 months.

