5.4.12 Data Viewing After 12 Months

Subjects in the Randomized Arm are required to remain in their assigned treatment group until they complete their 12 month visit. After the 12 month visit has been completed, at the clinicians' discretion, PA pressure readings for Control Group subjects can be made visible to the site through the Merlin.net™ website. To view data after the 12 month visit, contact the clinical technical support team who will arrange access to the data on the Merlin.net™ website and will review the waveforms to evaluate accuracy of the signal for any signs of drift. Upon initiating contact with clinical technical support, sites will be instructed to allow three working days for review.

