5.9 Subject Withdrawal

Subjects must be informed about their right to withdraw from the clinical trial at any time and for any reason without sanction, penalty or loss of benefits to which the subject is otherwise entitled. Withdrawal from the clinical trial will not jeopardize their future medical care or relationship with the Investigator. Subjects will be requested to specify the reason for the request to withdraw. The Investigator must make all reasonable efforts to retain the subject in the clinical trial until completion of the trial.

A subject will be considered 'Lost to Follow-up' after two missed visit(s) and a minimum of two unsuccessful phone calls from investigational site personnel to the subject or subject's contact to schedule the next follow-up visit. These two phone calls must be documented in the subject's hospital records. If the subject is deemed lost to follow-up a letter should be sent to the subject's last known address or to the subject's general practitioner and a copy of the letter must be maintained in the subject's hospital records.

If the subject requests to withdraw from the trial, the site should make attempts to schedule the subject for a final trial visit. If the subject agrees, then at this final trial visit, the subject will undergo the following assessments:

- Collect all reportable event information (see section 8.2.1) since the prior visit

[REDACTED]

[REDACTED]

- Medication review and documentation

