5.10.4 CEC

A CEC will be responsible for providing an independent review and adjudication of the following data:

- Events that could contribute to primary endpoints for either trial arm, to determine which events meet primary endpoint qualification, including:
 - All cardiovascular hospitalizations, cardiovascular emergency department visits, and cardiovascular hospital outpatient visits, all defined as a hospital visit with the primary cause being cardiovascular in nature, as reported by the Investigator
 - All deaths
 - Any hospitalizations which, when reviewed by the Sponsor, could potentially meet endpoint qualification
- HFHs that occurred within 12 months prior to baseline
- All events that could contribute to the secondary safety endpoint for either trial arm including ADEs, SADEs, and UADEs

All attempts will be made to blind the CEC to the treatment group assignment. The function, responsibilities and membership of the CEC will be described in greater detail in a CEC charter.

6 Statistical Considerations

The following section describes the statistical methods for the clinical trial and justification of the design. Additional details on statistical analyses, including sensitivity analyses, poolability analyses, subgroup analyses and analysis of descriptive endpoint(s) will be described in a separate Statistical Analysis Plan (SAP). Hypothesis tests will be 1-sided and conducted at a significance level of 2.5% unless stated otherwise.

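### Reporting of primary-endpoint events stops at withdrawal or when the investigator ends participation, with no stated capture to month 12, so follow-up after an event may be lost unequally by group

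*Protocol*

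**What the plan says.** **Endpoint and population.** CIP 4.3.1.1 defines the Randomized Arm's primary endpoint as recurrent HF hospitalizations, emergency or observation visits for intravenous diuretics, and all-cause death, to 12 months after implant. SAP 5.1.1.4 analyses everyone randomized. CIP 4.1.2 states "Each subject will be followed for 12 months, with follow-up visits at 6 and 12 months".

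**Reporting route.** CIP 8.2.1 makes hospital admissions, cardiovascular emergency or observation visits and deaths reportable. From these the Clinical Events Committee adjudicates the endpoint.

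**Stop rule.** CIP 8.2 continues surveillance and reporting until the last visit or death, or until "the subject's participation in the clinical trial is concluded by the Investigator, or the subject withdraws from the clinical trial". The public text lists no grounds on which an investigator may conclude participation.

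**Withdrawal.** CIP 5.9 requires reasonable efforts at retention and asks sites to try to arrange a final visit. If the subject agrees, the site is to "Collect all reportable event information (see section 8.2.1) since the prior visit" and review medication. No later collection of events or vital status is stated. SAP 6.3 summarizes withdrawals by reason.

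**Allocation and access.** The arm is single-blind: sites see uploaded pressures for Treatment subjects and not for Control subjects (CIP 4.1.2). CIP 5.4.12 says "Subjects in the Randomized Arm are required to remain in their assigned treatment group until they complete their 12 month visit"; Control uploads can be opened only after that visit.

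**The concern.** With a recurrent-event endpoint, the time after a first event carries endpoint information, and it carries most in the subjects at highest risk. A rule that stops collection when participation ends discards that time and any death within it. If exits follow HF events at the same rate in both groups, little harm results. If the rates differ, the group that loses more high-risk follow-up looks better than it is. Staff who decide or influence exits know the allocation, so equal rates cannot be taken for granted. No analysis method can restore events that were not collected. At stake are the primary hazard ratio and its power or its type I error, depending on which group loses more.

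**Working it through.** **Plan's own figure.** The Randomized Arm has "approximately 1000 subjects (following successful implantation and randomization, 500 per group) at approximately 140 sites". This number cannot be reproduced, because the power, assumed hazard ratio, event rates and dropout are redacted. The check is therefore a simulation of the mechanism.

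**Inputs from the documents.** 500 per group; 1:1 allocation ("be randomized in a 1:1 ratio into one of two groups", CIP 4.1.2); 12 months; one-sided 2.5% (opening of CIP section 6: "Hypothesis tests will be 1-sided and conducted at a significance level of 2.5% unless stated otherwise").

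**Assumed inputs.** Control HF-event rate 0.6 per year. HF-event rate ratio 0.75, or 1 under the null. Gamma frailty with variance 0, 1.5 or 3. Death hazard 0.09 per year times the square root of frailty, the same in both groups. After each HF event the subject leaves with probability p; that event counts, and later events and death do not. 1000 runs per setting.

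**Estimator.** In each group r = ΣE/ΣF (events over person-time). The log ratio is ln(r_T/r_C), with robust variance equal to the sum over groups of Σ(E − rF)²/(ΣE)². The null is rejected if z < −1.96. This corresponds to an Andersen–Gill fit with one covariate. The SAP's own model is redacted, so this choice is also an assumption.

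**Sanity checks without frailty.** The full-follow-up composite ratio should be near (0.6 × 0.75 + 0.09)/(0.6 + 0.09) = 0.54/0.69 = 0.783; the runs give 0.780 to 0.785. With p = 10%, the share of Control lost should be near 1 − exp(−0.10 × 0.6) = 5.8% before allowing for deaths; the runs give 5.5% to 5.6%.

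**Control-only loss, HF-event ratio 0.75:**

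| Frailty variance | p | Control lost | Ratio, full data | Ratio, observed | Power, full | Power, observed |
|---|---|---|---|---|---|---|
| 0 | 10% | 5.5% | 0.785 | 0.785 | 82.8% | 82.8% |
| 1.5 | 5% | 2.7% | 0.776 | 0.792 | 62.8% | 57.2% |
| 1.5 | 10% | 5.3% | 0.781 | 0.812 | 60.1% | 47.3% |
| 1.5 | 20% | 9.9% | 0.779 | 0.838 | 61.9% | 36.0% |
| 3 | 5% | 2.6% | 0.773 | 0.803 | 50.2% | 39.0% |
| 3 | 10% | 5.0% | 0.771 | 0.831 | 49.5% | 29.2% |
| 3 | 20% | 9.2% | 0.774 | 0.888 | 49.4% | 14.7% |

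**No effect (ratio 1), p = 10%:**

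| Who leaves | Frailty variance | Ratio, observed | One-sided rejection |
|---|---|---|---|
| Control only | 1.5 | 1.034 | 1.2% |
| Control only | 3 | 1.083 | 0.4% |
| Treatment only | 1.5 | 0.959 | 6.5% |
| Treatment only | 3 | 0.936 | 6.6% |
| Both | 1.5 | 1.009 | 2.7% |
| Both | 3 | 1.005 | 1.7% |

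The simulation error on a 2.5% rejection rate is √(0.025 × 0.975/1000) = 0.5 percentage points, so 6.5% is well outside chance.

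**Reading.** Without frailty, an earlier event says nothing about later risk, and rates per person-time stay unbiased. With frailty, subjects who have had an event are at higher risk. Removing their remaining time lowers the observed rate in the group that loses them.

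**The case against.** **The investigator clause may be innocent.** It sits in a section that covers every attempted implant. It may only describe planned exits, such as the end of the 30-day follow-up after a failed implant (CIP 5.4.4.1). That is possible, but the wording is not limited to those cases, and the withdrawal clause applies to randomized subjects in any event.

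**Retention is required, and the final visit closes the interval since the last visit.** Both are true. Neither covers the time from withdrawal to month 12.

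**Redacted text may deal with this.** Missing-data rules, sensitivity analyses, contact rules and CIP 5.6 on health-economic data are blacked out, and Appendix B lists a Virtual Research Data Center. Claims-based capture cannot be excluded. Primary events nevertheless need adjudication, and CIP 8.3 relies on site-supplied source documents for it.

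**The size is assumed.** This stands. If the pressure to leave affected only some Control subjects, say one third of those with events, and 30% of them left, the overall figure would be about 1/3 × 30% = 10%, the middle setting above. Smaller shares give smaller effects.

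**Stronger readings a reader might infer.** The approved indication covers "NYHA Class III HF patients who have been hospitalized for HF in the previous year". One might conclude that a Class III Control subject who qualified on natriuretic peptide and is then hospitalized can have pressure information used only by leaving the trial. The documents do not support this. Control management may take account of pressures from right heart catheterization (CIP 5.4.7), and clinically warranted repeat catheterization is foreseen in both groups (CIP 5.4.9). Deviations are possible in an emergency or with the required approvals (CIP 8.1), and nothing says that a deviation ends participation. No section says that withdrawal opens Control readings. What is barred before the 12-month visit is viewing the sensor uploads. Nor do CIP 5.4.12 and 8.2 contradict each other: one governs assigned management, the other reporting.

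**Conclusion.** The point stands as a gap in data collection. The public text ends reporting of primary-endpoint events at withdrawal or at an investigator decision for which it states no criteria, and it sets out no later capture to month 12. That does not fit well with a recurrent-event endpoint in all randomized subjects at sites that know the allocation.

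A reader might also infer that Control follow-up is in fact lost selectively, or that the gap favours the device. Neither is established. No withdrawal rate or pattern is public, and Control-only loss works against the device: in the middle setting, about 5% lost, the ratio rises by 0.03 to 0.06, power falls from 60% to 47% or from 50% to 29%, and null rejection drops to about 1% or less. A false claim of benefit becomes more likely only if Treatment loses more, with type I error about 6.5% in the same setting. These figures rest on the assumed rates, frailty and exit probabilities. Without frailty Control-only loss gives no bias, and equal loss in both groups gives little. The change is worth making because it is cheap and protects in either direction.

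**What to change.** In CIP 5.9 and 8.2, separate stopping assigned management, or an investigator decision, from withdrawal of consent for follow-up:

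1. For randomized subjects, an investigator decision or a deviation, including early viewing of Control readings, does not end endpoint reporting. HF hospitalizations, intravenous-diuretic visits and deaths are collected to 12 months and analysed by randomized group.
2. A subject who withdraws is asked for permission to collect vital status and HF hospital or emergency visits from records to 12 months.
3. SAP 6.3 tabulates withdrawals by randomized group and by whether an HF event came first.

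If a redacted section already provides this capture, 5.9 and 8.2 should refer to it. The cost is CIP and consent wording and modest chart review for the subjects concerned, with no new visits or procedures. Some subjects will refuse, so the gap narrows but does not close. No position is taken on when Control readings should be released.
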